### 11.9.2 ECG

QTcF values based on Fridericia's formula will be calculated as described in [Section 8.2.11](#) and then rounded to integer values. These integer values will be categorized into the following ranges: <450, 450-480, >480-500, and >500 msec. Changes from baseline in QTcF values will be categorized into: 31-60 and >60 msec.

The mean of the triplicate values at each time point will be used for the analyses of continuous ECG parameters. A summary of the ECG data and their corresponding change from baseline will be provided. A shift in QTcF table will include shifts to the highest post-baseline that includes data from both scheduled and unscheduled visits. Categories of each grade as defined above will be shown for baseline and post-baseline, with the number and percentage of subjects in each. In addition, the changes in QTcF categories as defined above will be summarized at each scheduled visit and at the highest post-baseline. Subjects must have a baseline and at least one non-missing post-baseline assessment in order to be included in the shift analysis.

The following summaries will be provided:

- Summary of Change from Baseline in ECG by Visit
- Shifts in QTcF from Baseline to the Highest Post-Baseline
- QTcF Increase from Baseline to the Highest Post-Baseline

The following listing will be provided:

- ECG

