19. Every 3 months during the Active Follow-up period and the samples should be collected at the closest Active follow-up visit.
20. Maintenance doses of IMO-2125 should be administered as per dosing instructions (see Section 9.3.3.2).
21. Follow-on anticancer treatment information will be collected during the telephone calls
22. Week 1 performed pre-dose (within 1.5 hours of dosing IMO-2125) and 1 hour (± 30 minutes) post-dose. Week 11 performed pre-dose (within 1.5 hours of dosing IMO-2125) and 1 hour (± 30 minutes) post-dose. ECGs should be done in triplicate.

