12.3.2. Electrocardiogram Monitoring

A resting 12-lead ECG will be performed (in triplicate for Arm B only) at intervals as specified in the Schedule of Evaluations ([Table 1](#) and [Table 2](#)). Any clinically significant findings during the Screening Visit should be recorded as part of the medical history.

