### **8.2.5 Baseline Definition**

Baseline is defined as the most recent, non-missing value prior to the first study treatment dose date and time. For enrolled subjects who did not receive study treatment during the study, baseline is defined as the latest, non-missing collected value before the date of randomization.

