#### **8.2.9 Other Assessments**

All data will be reported according to the nominal visit for which it was reported (that is, no visit windows will be applied during dataset creation). Unscheduled data will only be included in summaries of worst-case (highest and/or lowest) post-baseline assessments.

If multiple safety assessments on different days are reported for the same scheduled assessment, then the latest assessment for that scheduled assessment will be analyzed.

If multiple assessments are reported on the same date for the same scheduled planned time, then the worst-case result will be analyzed.

Data from all assessments (scheduled and unscheduled), including multiple assessments, will be included in listings.

Idera Pharmaceuticals, Inc.  
 Statistical Analysis Plan  
 Protocol Number: 2125-MEL-301

---

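### The QTcF highest-post-baseline tables set up to five triplicate time points in Arm B against one single tracing in Arm A, and the SAP does not say which triplicate rule feeds them.

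*SAP*

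**What the plan says.** **Statistic.** SAP 11.9.2 defines the shift table by the maximum: "A shift in QTcF table will include shifts to the highest post-baseline that includes data from both scheduled and unscheduled visits". For increases, "the changes in QTcF categories as defined above will be summarized at each scheduled visit and at the highest post-baseline". The bands are <450, 450-480, >480-500 and >500 ms for values, and 31-60 and >60 ms for increases.

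**Schedule.** Protocol Table 1 gives Arm A an ECG at Weeks 1 and 14. Table 2 gives Arm B Weeks 1, 11, 16 and 24. Footnote 22 splits two of those visits: "Week 1 performed pre-dose (within 1.5 hours of dosing IMO-2125) and 1 hour" post-dose, and "Week 11 performed pre-dose (within 1.5 hours of dosing IMO-2125) and 1 hour" post-dose. On replicates, Protocol 12.3.2 says "A resting 12-lead ECG will be performed (in triplicate for Arm B only" (the parenthesis closes there).

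**Baseline.** SAP 8.2.5: "Baseline is defined as the most recent, non-missing value prior to the first study treatment dose date and time". The Arm B Week 1 one-hour ECG therefore counts as post-baseline.

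**Triplicates.** Two rules could apply. SAP 11.9.2 says "The mean of the triplicate values at each time point will be used for the analyses of continuous ECG parameters" and does not mention the categorical tables. SAP 8.2.9 says "If multiple assessments are reported on the same date for the same scheduled planned time, then the worst-case result will be analyzed" and does not exempt ECG.

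**Outputs.** In SAP 16.2, Table 14.3.9.5 (QTcF increase, titled for the highest post-baseline value) is the only ECG output marked for the IDMC. The by-visit table 14.3.9.3, the shift table 14.3.9.4 and the ECG listing are marked for the ORR and final analyses only.

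**The concern.** The expected maximum of a set of noisy readings rises with the number of readings. A table that sets a maximum over several time points in one arm beside a single reading in the other mixes any drug effect with the sampling schedule. These tables are where a reader or the IDMC would look for a QT effect of IMO-2125. A sampling artefact there could pass for a signal or, where averaging quietens one arm only, hide one. The unsettled triplicate rule compounds this, because two programmers following the SAP could produce materially different tables from the same data.

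**Working it through.** The documents state no QTcF rate or variance, so there is no plan figure to reproduce. The counts come from the documents. The rates rest on assumed variances.

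**1. Scheduled post-baseline ECGs**

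- Arm A: Week 14 = 1 time point x 1 tracing = 1 (taking the Week 1 ECG as pre-dose).
- Arm B: Week 1 +1 h, Week 11 pre-dose, Week 11 +1 h, Week 16, Week 24 = 5 time points. With 12.3.2 (triplicate throughout), 5 x 3 = 15 tracings. If only the footnote 22 visits are triplicate, 3 x 3 + 2 = 11.

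So the maximum in Arm B runs over 5 means (11.9.2 averaging) or up to 15 tracings (8.2.9), against 1 value in Arm A.

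**2. Model with no drug effect**

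QTcF = subject + occasion + replicate error, all normal, rounded to whole ms. Assumed: mean 415 ms, between-subject SD 15, occasion SD *sb*, replicate SD *sr*, independent occasions, every scheduled ECG done, no unscheduled ECGs. There were 400,000 simulated subjects per arm. In the last two columns the Arm B baseline is either the triplicate mean or the worst of three.

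| sb/sr | >=450: A | >=450: B, 5 means | >=450: B, 15 tracings | Incr. >=31: A | Incr. >=31: B, 5 means | Incr. >=31: B, 15, mean base | Incr. >=31: B, 15, worst base |
|---|---|---|---|---|---|---|---|
| 8/4 | 2.4% | 6.0% | 9.3% | 0.8% | 2.0% | 4.7% | 2.4% |
| 8/6 | 2.8% | 6.5% | 12.4% | 1.6% | 2.8% | 8.6% | 3.9% |
| 12/5 | 4.1% | 12.0% | 18.2% | 4.9% | 13.8% | 21.6% | 14.6% |
| 7/7 | 2.7% | 5.8% | 12.7% | 1.5% | 1.7% | 7.8% | 2.9% |
| 5/10 | 3.3% | 5.3% | 17.1% | 2.7% | 1.0% | 12.5% | 3.6% |
| 4/8 | 2.4% | 3.9% | 11.2% | 0.8% | 0.1% | 3.1% | 0.7% |

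With between-subject SD 16 and *sb/sr* of 6/5, 8/6 and 10/6, the >=450 ms rates are 2.6-4.1% in Arm A, against about 5-10% (5 means) or 9-17% (15 tracings) in Arm B. At 6/5, increases >=31 ms are 0.3% in both arms on the 5-means reading.

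**3. Why the increase table can go either way**

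The SD of one change from baseline is sqrt(2(sb² + sr²)) in Arm A and sqrt(2(sb² + sr²/3)) for a triplicate mean in Arm B. After rounding, the threshold is 30.5 ms.

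- *5/10.* Arm A: sqrt(250) = 15.8, 30.5/15.8 = 1.93, tail 2.7%. Arm B: sqrt(116.7) = 10.8, 30.5/10.8 = 2.82, tail 0.24% per time point. Five time points give at most 5 x 0.24% = 1.2%, below Arm A.
- *12/5.* Arm A: sqrt(338) = 18.4, tail 4.9%. Arm B: sqrt(304.7) = 17.5, tail 4.0% per time point. Averaging gains little and five tries dominate (13.8% simulated).

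**4. Less favourable attendance**

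With same-day correlation 0.5 and attendance of 70%, 45% and 35% at Weeks 11, 16 and 24 (also assumed), between-subject SD 16 and the 5-means reading:

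- >=450 ms: 2.6-4.1% in Arm A against 4.1-7.3% in Arm B.
- Increase >=31 ms, at 6/5, 8/6 and 10/6: 0.3% vs 0.1%, 1.5% vs 1.3%, 3.2% vs 3.8%.

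**5. Higher bands**

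Even with 15 tracings and full attendance, values above 480 ms stay at or below about 0.4% in Arm B at SDs 6/5, 8/6 and 10/6. Increases above 60 ms stay below 0.5% in every scenario.

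**6. Entry to the tables**

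SAP 11.9.2 requires a baseline and one post-baseline value for the shift analysis. Arm B subjects qualify from the Week 1 one-hour ECG. Arm A subjects need Week 14 or an unscheduled ECG. The denominators therefore differ as well.

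**The case against.** Four counter-arguments deserve weight.

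*The section-specific rule should govern.* The averaging sentence sits in the same paragraph as the shift table, and QTcF is a continuous parameter, so the natural reading may be 5 means. A reader might infer that the maximum certainly runs over 15 tracings. The documents do not support that as fact. It follows only if 8.2.9 overrides 11.9.2 for the categorical tables, and the SAP does not say. What stands is the ambiguity.

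*An excess in the IDMC table is not assured.* A reader might infer that Arm B must show more increases >=31 ms. On the 5-means reading the excess can be absent or reversed, so only the possibility of bias in either direction is established.

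*Other displays exist.* A reader might infer that an artefact could never be told from a real effect. That goes too far: change categories and mean changes by visit are planned, and ECGs are listed. But no post-baseline ECG week is common to both arms, 8.2.9 applies no visit windows, and the table marked for the IDMC is titled for the maximum. The mock displays are in separate documents, so whether it also carries the by-visit categories cannot be seen.

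*The stakes are modest.* Protocol 15.5 makes the safety analyses descriptive, no decision rule uses the maximum, and the higher bands scarcely move. This is correct and limits the weight of the point, but does not remove it.

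**Conclusion.** The point holds in a limited form. The unequal ECG schedule is plain in the documents, and 11.9.2 does nothing to offset it. In every scenario tried, on either triplicate reading, the >=450 ms category was higher in Arm B with no drug effect: roughly double to two and a half times Arm A with averaged triplicates at SDs of 6/5 to 10/6, and about four times with worst-of-three. Incomplete attendance and same-day correlation reduce this. The >=31 ms increase category can be biased up or down, depending on the triplicate rule and on whether replicate or occasion noise dominates. The >480 ms and >60 ms bands are little affected. All rates rest on assumed means and SDs; the counts and the unresolved triplicate rule do not. It is worth correcting before the tables are produced, but does not threaten the trial's main conclusions.

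**What to change.** In SAP 11.9.2:

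- (a) Use the triplicate mean for baseline and post-baseline in all Arm B categorical QTcF tables, and exempt ECG triplicates from the 8.2.9 worst-case rule.
- (b) Keep the highest-post-baseline tables, label them as not comparable between arms, and show the number of ECG time points per subject.
- (c) Add a between-arm category table at the nearest visits, Arm A Week 14 and Arm B Week 16. Use one tracing per arm at both baseline and post-baseline (the first of the triplicate in Arm B), as a stated exception to (a). Supply it to the IDMC with 14.3.9.5. At a single visit with one tracing per arm, the no-effect rates equalise (3.3% vs 3.3% for >=450 ms at 8/6).
- (d) Show Arm B Week 1 and Week 11 one-hour changes from the same-day pre-dose ECG. The comparison in (c) may miss an acute effect: Week 16 is five weeks after the scheduled Week 11 dose, and the timing of its ECG relative to that day's dose is not specified.

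The cost is SAP wording and a few table shells, with no new ECGs. The downside is that the matched comparison rests on one late, single-tracing time point, so it is less precise and cannot be the only between-arm view.

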## 12 PHARMACOKINETIC ANALYSES

For subjects in the ipilimumab + IMO-2125 arm, all subjects who received at least one dose of IMO-2125 with at least one measurable concentration of IMO-2125 will be included in the PK Analysis Set. Blood samples will be drawn for determination of IMO-2125 plasma concentrations at pre-dose, and at 1, 2, and 4 hours post-dose at Week 1 and Week 11. Descriptive summary statistics (number of non-missing observations (n), arithmetic mean, standard deviation, % coefficient of variation (CV) (which is 100\* standard deviation/mean), median, minimum, maximum, geometric mean and geometric % CV will be reported for concentration values grouped by week and collection time point. For the calculation of mean concentrations, all concentrations below the Lower Limit of Quantification (LLOQ) will be treated as zero.

Idera Pharmaceuticals, Inc.  
 Statistical Analysis Plan  
 Protocol Number: 2125-MEL-301

---

The following summary table will be provided:

- Summary of Pharmacokinetic Concentrations

Individual IMO-2125 values (by week, nominal and actual sampling time points) will be listed for all subjects. Other PK analyses are outside the scope of this SAP and will be described in a separate analysis plan. The following listing will be provided:

- Pharmacokinetic Concentrations

## **13 PATIENT-REPORTED QUALITY OF LIFE**

All analyses of patient-reported quality of life data will be descriptive. No p-values will be calculated; point and interval estimates will be reported. All QoL tables, listings, and figures will use the ITT Analysis Set.

The five functional scales (physical, role, cognitive, emotional, and social), three symptom scales (fatigue, pain, and nausea and vomiting), global health status / QoL scale, the single items assessing additional symptoms commonly reported by cancer patients (dyspnoea, loss of appetite, insomnia, constipation, and diarrhoea) and perceived financial impact of the disease, will be scored. At the time of this SAP, it is noted that some subjects under protocol version 2 collected QoL data on paper and/or a mixture of paper and electronic media. For that reason, all the analyses described below, unless stated otherwise, will be done for paper PROs and electronic-PROs (ePROs) separately. In addition, the analyses will be repeated with combined paper PRO and ePRO data.

### **13.1 SCORING THE EORTC QLQ-C30 RESULTS**

The five functional scales (physical, role, emotional, cognitive, and social), three symptom scales (fatigue, pain, and nausea and vomiting), global health status / QoL scale, and single items assessing additional symptoms commonly reported by cancer patients (dyspnoea, insomnia, appetite loss, constipation and diarrhoea) and perceived financial impact of the disease will be scored. Scoring of all scales will use the EORTC QLQ-C30 Scoring Manual instructions for version 3.0 of the QLQ-C30 instrument.

Let  $I_i$  be the score for the  $i^{\text{th}}$  item on the QLQ-C30 instrument,  $i=1, 2, 3, \dots, 30$ , ranges be the difference between the possible maximum and the minimum response to individual items for scale  $s$ , and  $n_s$  be the number of items on the scales.

For all scales, the Raw Score,  $RS_s$ , is the mean of the component items:

$$\text{Raw Scores}_s = RS_s = (I_1 + I_2 + \dots + I_{n_s}) \div n_s$$

Idera Pharmaceuticals, Inc.  
 Statistical Analysis Plan  
 Protocol Number: 2125-MEL-301

---

Then for **Functional scales**:

$$\text{Score}_s = \{1 - (\text{RS}_s - 1) \div \text{range}_s\} \times 100$$

and for **Symptom scales/items** and the **Global health status /QoL**:

$$\text{Score}_s = \{(\text{RS}_s - 1) \div \text{range}_s\} \times 100.$$

Global health status / QoL	Scale	Number of Items	Range	V3.0 Item Numbers
Global health status/QoL	QL2	2	6	29, 30
Functional scales				
Physical functioning	PF2	5	3	1 to 5
Role functioning	RF2	2	3	6, 7
Emotional functioning	EF	4	3	21 to 24
Cognitive functioning	CF	2	3	20, 25
Social functioning	SF	2	3	26, 27
Symptom scales / items *				
Fatigue	FA	3	3	10, 12, 18
Nausea and vomiting	NV	2	3	14, 15
Pain	PA	2	3	9, 19
Dyspnoea	DY	1	3	8
Insomnia	SL	1	3	11
Appetite loss	AP	1	3	13
Constipation	CO	1	3	16
Diarrhoea	DI	1	3	17
Financial difficulties	FI	1	3	28

\* Item range is the difference between the possible maximum and the minimum response to individual items; most items take values from 1 to 4, giving range = 3.

## 13.2 SUMMARY OF EORTC QLQ-C30 RESULTS

EORTC QLQ-C30 scores for each scale and single-item measure will be summarized by baseline and all scheduled visits using the total number of subjects with a measurement on that scale at that visit, the mean, standard deviation, median, minimum, and maximum. These summaries will also report change from baseline using the same descriptive statistics. Box and whisker plots of change from baseline for each scale by visit will also be produced.

The following summary and figure will be produced:

- Summary of Change from Baseline in EORTC QLQ-C30 Assessment Scores by Visit Using ePRO, Paper PRO and Combined ePRO and Paper PRO Data

Idera Pharmaceuticals, Inc.  
Statistical Analysis Plan  
Protocol Number: 2125-MEL-301

---

- Line Graph of Mean (+/-SE) Change from Baseline in EORTC QLQ-C30 Scores and Sub-Scale by Visit Using ePRO, Paper PRO and Combined ePRO and Paper PRO Data

The listing to be produced is:

- EORTC QLQ-C30 Assessments Scores Using ePRO, Paper PRO and Combined ePRO and Paper PRO Data

### **13.3 ANALYSIS OF CHANGE FROM BASELINE IN EORTC QLQ-C30 SCORES**

The change from baseline in each EORTC QLQ-30 multi-item scale and single-item measures will be analyzed over all post treatment assessment time points using a mixed effect model for repeated measures (MMRM). The combined data from both paper PRO and ePRO will be used for this analysis. The main MMRM model will include treatment, visit, and treatment-by-visit timepoint interaction term as fixed effects, and stratification factors and baseline score as a covariate.

Due to differences in the visit schedules for the treatment arms, Weeks 7 and 8 will be treated as the same visit. The model-based point estimates including least squares (LS) means, treatment difference in the LS means, and 2-sided 95% CI for the difference for each visit will be reported.

For each MMRM model, select the optimal model covariance structure according to the following steps. Note that if the SAS log contains “converge criteria not meet”, “G matrix (or D or Hessian) is not positive definite”, that model is considered not fitted.

1. Use an unstructured covariance structure without a random subject effect.
2. Use a spatial power covariance structure with a random subject effect

If both these models can be fitted, choose the model with smaller AIC. If only one model is fitted, the fitted model will be the model selected.

If neither of these models can be fitted, then try the next three options in order. Stop at the first model to be fitted.

3. Use an autoregressive(1) covariance structure with a random subject effect.
4. Use an autoregressive(1) covariance structure without a random subject effect.
5. Use a compound symmetric covariance structure without a random subject effect.

Idera Pharmaceuticals, Inc.  
 Statistical Analysis Plan  
 Protocol Number: 2125-MEL-301

---

If no model fits for a given analysis, do not produce any output.

The generic SAS procedure call is

```
proc mixed data=<SAS dataset name>;
  class treatment visit subject;
  model <change in scale name> = strata baseline visit treatment
    visit*treatment;
  random subject;
  repeated visit / subject=usubjid type=UN;
  lsmeans visit*treatment / diff=all cl alpha=0.05;
run;
```

The following summary will be produced:

- MMRM Analysis of Change from Baseline in EORTC QLQ-C30 Assessment Scores by Visit Using Combined ePRO and Paper PRO Data

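### The generic SAS call for the quality-of-life MMRM matches none of the SAP's five covariance steps and omits strata and the subject identifier from CLASS

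*SAP*

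**What the plan says.** SAP 13.3 describes an MMRM for change from baseline in each QLQ-C30 scale and item. Its text and its code bear on the point as follows.

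- **Step 1 of the covariance choice:** "Use an unstructured covariance structure without a random subject effect".
- **Step 2:** "Use a spatial power covariance structure with a random subject effect". If both steps fit, the smaller AIC decides; if only one fits, it is used. Steps 3 to 5 are tried in order only if both fail: AR(1) with a random subject effect, AR(1) without one, and compound symmetry without one.
- **Failure rule:** if the SAS log reports non-convergence, or a G, D or Hessian matrix that is not positive definite, "that model is considered not fitted".
- **Code:** one call, labelled generic. It contains "random subject" as a RANDOM statement together with "repeated visit / subject=usubjid type=UN". Its CLASS statement is "class treatment visit subject" and its MODEL statement begins "model <change in scale name> = strata baseline visit treatment".
- **Model terms in the text:** treatment, visit and their interaction, plus "stratification factors and baseline score as a covariate".

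SAP 8.2.10 defines the analysis strata as four cells: M1c or other, crossed with BRAF positive or wild type. Protocol 15.4.2 says the stratification factors in this model are those used in the primary OS analysis.

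**The concern.** The printed call is the only code given for this analysis, and it disagrees with the text beside it. The disagreement touches the model-selection rule, because the extra RANDOM statement makes the covariance model redundant and the usual sign of redundancy is the message that the SAP treats as a failed fit. The least restrictive structure could then be lost because of a coding slip and not because of the data. Separately, a nominal four-level factor that is missing from CLASS is not adjusted for as a factor. The covariance structure and the strata adjustment both feed the LS-mean differences and confidence intervals that this section reports.

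**Working it through.** **1. Code against steps.** The call has a random subject effect and UN. Step 1 is UN without the random effect. Steps 2 and 3 have the random effect but use spatial power and AR(1). Steps 4 and 5 have no random effect. The printed combination is therefore none of the five.

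**2. Identifiability.** With t visits, UN has t(t+1)/2 free parameters. A random subject intercept adds σ_b²J, where J is the t×t matrix of ones, so V = σ_b²J + R with R unstructured. The derivative of V with respect to σ_b² is J. J is the sum of the derivative matrices for all the UN elements, so the extra column of information is a linear combination of the others. The rank of the expected information, ½·tr(V⁻¹D_iV⁻¹D_j), was computed as a check. The schedule has 7 post-baseline PRO visits in the first year (Week 7 or 8, then 12, 20, 28, 36, 44 and 52). Adding four 12-weekly visits gives 11.

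| Visits | UN: rank / parameters | UN + random subject: rank / parameters |
|---|---|---|
| 3 | 6 / 6 | 6 / 7 |
| 7 | 28 / 28 | 28 / 29 |
| 11 | 66 / 66 | 66 / 67 |

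The same deficit of one appears under monotone dropout (6 of 7 for 3 visits, 28 of 29 for 7). In one simulated data set (4 visits, n = 200), the minimised −log L was 2148.8793 at each of σ_b² = 0, 5, 10, 20, 30 and 40. The likelihood is flat in the extra parameter.

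**3. Consequence under the SAP's rule.** A flat direction would be expected to show as a singular Hessian, or as a subject variance set to zero with G not positive definite. Either message meets the failure rule. Step 2 would then be the only fitted model if it converges, and no AIC comparison would take place. If RANDOM were also left in for later steps, step 4 would become step 3. Step 5 would be redundant in the same way as step 1, because compound symmetry also contains J.

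**4. CLASS statement.** Strata is in MODEL but not in CLASS. Two cases are possible:

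- *Numeric code 1 to 4:* one linear slope, 1 df, instead of 4 − 1 = 3 df.
- *Character variable:* the procedure stops with an error.

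The subject identifier has a similar fault. REPEATED uses usubjid, while CLASS lists a different name, subject. A character usubjid would also stop the run.

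**5. Size of the strata effect if the code is numeric.** The documents give no SD or stratum effects, so these are assumptions: one visit, N = 454, residual SD 20, four equal strata.

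- With class strata, the SE of the treatment difference is about 2 × 20/√454 = 1.88.
- With a numeric code, the stratum variance v left unexplained by a straight line is added to the residual, so the SE is multiplied by √(1 + v/400).
- Stratum effects of 0, 10, −10 and 5 have squared deviations summing to 218.75. The slope explains 1.25, so v = 217.5/4 = 54.4 and the factor is 1.07, giving an SE of 2.00.
- Halving those effects gives v = 13.6 and a factor of 1.02. With no stratum effects, or exactly linear ones, the factor is 1.00.

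A simulation of the first case gave mean SEs of 2.00 and 1.87, with mean treatment estimates of 0.07 and −0.05 against a true value of 0. On these assumptions the loss is in precision, from 0 to about 7%, and there is no bias.

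**The case against.** The call is labelled generic and contains placeholders. One call cannot serve five covariance models, so RANDOM and the covariance type have to change from step to step, and the numbered text says when the random effect is present. The failure rule applies to the listed steps. Since UN with RANDOM is not one of them, its failure does not make step 1 a failure. This stands. A reader might infer that the code will probably force UN to be rejected. The documents do not support that, because a programmer working from the numbered steps would drop RANDOM for step 1.

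A literal run might also never reach the covariance message. If strata or usubjid is a character variable, the procedure stops visibly and someone corrects the code. The variable types are not given, and SAP 8.2 leaves derivation details to separate dataset specifications. A reader might also infer that strata will in fact be fitted with 1 df. That holds only for a numeric code, which no section specifies. The phrase "stratification factors and baseline score as a covariate" is loose, so the omission from CLASS conflicts more clearly with the four nominal cells in SAP 8.2.10 than with the text of 13.3.

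One further complaint has no basis. The text already promises treatment differences with 95% intervals at each visit, so nothing is missing there.

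None of this makes the call correct. It matches no planned model, and its CLASS list is incomplete.

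**Conclusion.** The point holds as a mismatch between code and text in a prespecified analysis. The redundancy of UN plus a random subject intercept is exact: one parameter too many at every number of visits. What follows is conditional. If the call were used literally for step 1, it could either stop with an error or trigger the SAP's failure rule, leaving spatial power without the AIC comparison. If the steps are followed, UN is fitted as intended. The 1 df instead of 3 depends on a numeric strata code and on the four cells of SAP 8.2.10 being the strata meant. The SE loss of 0 to about 7% depends on the assumed SD and stratum effects. SAS itself was not run.

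The reach is the MMRM for 15 scales and items (1 global, 5 functional, 9 symptom or single items) in Table 14.5.1.4. SAP 13 makes these analyses descriptive, without p-values. The tests of ORR and OS and the alpha allocation are untouched. This is a minor correction, worth making because it removes a choice between two readings of the plan.

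**What to change.** Amend the code in SAP 13.3 to match its own steps:

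- Use `class treatment visit strata usubjid;` and the same subject identifier in every statement.
- Remove RANDOM from the calls for steps 1, 4 and 5.
- Give separate calls for steps 2 and 3, the only ones with a random subject effect.
- State in the text that strata enter as a classification factor using the four cells of SAP 8.2.10.

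The cost is a few lines of SAP text and code before database lock. No new data, design change or change to the selection rule is needed.
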